
Study Design

Phase*

Not applicable

Design

General Design: A randomized, controlled trial in non-acute postpartum anemia comparing single-unit versus multiple-unit transfusion by total numbers of units transfused. Allocation to Interventional Group: Subjects will be randomized to either single-unit versus multiple-unit transfusion protocols. Subjects will be randomized in a one to one fashion and the randomization will take place using a computer-generated algorithm. Study Measures 1. The Edinburgh Postnatal Depression Scale (EPDS) is a 10-item self-report scale designed to screen for postnatal depression. It has been validated in large, diverse populations over the last 30 years (10-11). The scale can be completed in about 5 minutes and has a simple method of scoring. It has a score that ranges from 0 to 30. Mothers will be considered to have possible postpartum depression (PPD) when the EPDS score is 11. The cutoff will be set at 11, as studies have shown this cutoff to maximize the sensitivity and specificity in detecting PPD to 100 and 92 %, respectively (12). 2. The Multidimensional Fatigue Inventory (MFI) evaluates five dimensions of fatigue: general fatigue, physical fatigue, reduced activity, reduced motivation and mental fatigue. The MFI has previously been evaluated in a postpartum population, where the findings demonstrated a significant correlation between hemoglobin and physical fatigue score (13). The MFI consists of 20 statements for which the participant indicates, on a 5-point scale, the extent to which the particular statement applies with regard to aspects of fatigue experienced during the previous days. Higher scores indicate a higher degree of fatigue. The minimum clinically relevant difference for the MFI has not been established for women in the puerperium. 3. The Maternal Attachment Inventory (MAI) was developed to measure maternal affectionate attachment (14). This is the unique, affectionate relationship that develops between a woman and her infant. It consists of 26 items, organized into a four-point Likert scale. t. The lowest score is 26, and the highest is 104. Higher scores indicate greater attachment between mother and baby. Primary Study Endpoint: The primary study endpoint will be a reduction in number of blood products used per person from 1.9 to 1.75 with a SD of 0.5.

Study duration

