In order to determine our expected sample size, we assessed our baseline data (15). During this time period, the culture at our institution was that if the decision was made to proceed with transfusion, generally 2 units of pRBCs were given. Over a 3 month period in 2015, 612 patients delivered, of which 30 received pRBC transfusions (4.9%). 11 of these transfusions occurred prior to the 12 hour blood count, which may indicate a more acute need for transfusion. Some of those patients may have also received additional units in the non-acute setting after stabilization and thus would still qualify to participate in this study. In the whole group of transfused patients, a total of 74 units of pRBCs were transfused, at an average of 2.5 units per person transfused. Excluding those transfused in the first 12 hours postpartum, 36 units of pRBCs were transfused among 19 patients at an average of 1.9 units per person transfused (with a standard deviation [SD] of 0.3). Thus, over one year, we would expect to see approximately 72 patients requiring non-acute postpartum transfusion. Our expected sample size to have 80% power to demonstrate a reduction in number of blood products used per person from 1.9 to 1.68 with a SD of 0.5, assuming an alpha of 5%, would be 33 patients per group. If 50% of patients agreed to participate, we estimate it will take 2 years to achieve this sample size. We then expect it will take an additional year to analyze and publish our data. For each study participant, they will be involved in the study from the time of consent until their 4-9 week postpartum visit. In order to reduce burden to patients, we plan to combine our postpartum survey instruments with the routine postpartum visit.

Resources necessary for human research protection

Describe research staff and justify that the staff are adequate in number and qualifications to conduct the research. Describe how you will ensure that all staff assisting with the research are adequately informed about the protocol and their research related duties. Please allow adequate time for the researchers to conduct and complete the research. Please confirm that there are adequate facilities for the research.

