Given we expect to enroll approximately 3 patients per month, the overall burden on the research staff is minimal. Consent and randomization will be performed by the primary investigators as well as trained housestaff who are generally responding to the need for transfusion. 1-2 training sessions will occur prior to the beginning of study to adequately train involved housestaff for the consenting process and the research protocol. Ongoing educational modules will take place throughout the course of the study and additional training sessions will occur to address housestaff turnover.

Characteristics of the Study Population

Target population

We would include nonacute postpartum women (defined as 6 hours after delivery) who have been determined to require blood transfusion either by Hb 7g/dL, or 7g/dL with signs or symptoms of anemia such as fatigue, dizziness, tachycardia, or hypotension.

Subjects enrolled by Penn Researchers

66

Subjects enrolled by Collaborating Researchers

0

Accrual

We plan to recruit admitted postpartum patients at the time a provider makes the decision that they require a nonacute blood transfusion. In order to determine our expected sample size, we assessed our baseline data (15). During this time period, the culture at our institution was that if the decision was made to proceed with transfusion, generally 2 units of pRBCs were given. Over a 3 month period in 2015, 612 patients delivered, of which 30 received pRBC transfusions (4.9%). 11 of these transfusions occurred prior to the 12 hour blood count, which may indicate a more acute need for transfusion. Some of those patients may have also received additional units in the non-acute setting after stabilization and thus would still qualify to participate in this study. In the whole group of transfused patients, a total of 74 units of pRBCs were transfused, at an average of 2.5 units per person transfused. Excluding those transfused in the first 12 hours postpartum, 36 units of pRBCs were transfused among 19 patients at an

average of 1.9 units per person transfused (with a standard deviation [SD] of 0.3). Thus, over one year, we would expect to see approximately 72 patients requiring non-acute postpartum transfusion. Our expected sample size to have 80% power to demonstrate a reduction in number of blood products used per person from 1.9 to 1.68 with a SD of 0.5, assuming an alpha of 5%, would be 33 patients per group.

Key inclusion criteria

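### The planning mean (1.9) and baseline SD (0.3) come from a narrower group than the trial enrols, and 33 per group matches an SD near 0.315, not the stated, unsourced 0.5

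*Combined protocol and SAP*

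**What the plan says.** Study duration, repeated under Accrual, describes a three-month audit from 2015. Thirty women were transfused with 74 units in total. Eleven of the transfusions came before the 12-hour blood count. The planning baseline leaves those out: "Excluding those transfused in the first 12 hours postpartum, 36 units of pRBCs were transfused among 19 patients", reported as a mean of 1.9 with an SD of 0.3. Of the omitted women the protocol says: "Some of those patients may have also received additional units in the non-acute setting after stabilization and thus would still qualify to participate".

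Target population uses a different time limit: "We would include nonacute postpartum women (defined as 6 hours after delivery". Key inclusion criteria repeats 6 hours. The comparison sign is missing from the text available to me; I read it as 6 hours or more.

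The sample-size sentence plans for 80% power and a "reduction in number of blood products used per person from 1.9 to 1.68 with a SD of 0.5", and concludes "assuming an alpha of 5%, would be 33 patients per group". No source is given for 0.5. The Design section gives another target for the same endpoint: "reduction in number of blood products used per person from 1.9 to 1.75 with a SD of 0.5". The Analysis Plan names a t test. The primary outcome is the total number of units transfused, and the text does not say from what moment units count.

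**The concern.** A sample size for a comparison of means depends on the SD in the women who will be randomised. Here the only SD with a data source belongs to women not transfused before 12 hours. Women first transfused between 6 and 12 hours can enter the trial but are absent from the baseline, as are women who had an early acute transfusion and later needed more blood. The protocol notes the second group and makes no adjustment for it.

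The SD in the calculation, 0.5, is not the baseline SD and is not explained. A reader cannot tell whether it is meant as an allowance for the wider population or is a slip. If the figure of 33 was in fact worked out from the narrow group's spread, any such allowance never reached the enrolment target. At stake is whether 66 women can answer the primary question, and whether a null result could be interpreted.

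**Working it through.** **Inputs.** From Study duration: 30 women and 74 units overall; 19 women and 36 units after the exclusion; baseline SD 0.3; stated SD 0.5; means 1.9 and 1.68, so a difference of 0.22; alpha 5%; power 80%; 33 per group. From Design: means 1.9 and 1.75, so a difference of 0.15. Sidedness is not stated; I take two-sided and check one-sided.

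**Step 1: the omitted women.** 30 − 19 = 11 women and 74 − 36 = 38 units, so 38/11 = 3.45 units each, against 36/19 = 1.89 in the planning group. The 3.45 covers all their units, acute ones included.

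**Step 2: the plan's own figure.** n per group = 2 × SD² × (1.960 + 0.842)² / difference², where (1.960 + 0.842)² = 7.85.

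- Stated SD 0.5: 2 × 0.25 × 7.85 / 0.0484 = 81.1, so 82 per group (83 with the t distribution). One-sided: 64 (65).
- Baseline SD 0.3: 2 × 0.09 × 7.85 / 0.0484 = 29.2, so 30 (31 with t).
- SD 0.315: 2 × 0.0992 × 7.85 / 0.0484 = 32.2, so 33. The t-based value is 33.2, and power at 33 is 79.8%.

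The value 0.315 is the sample SD if 17 of the 19 women had 2 units and 2 had 1 unit. That split is my assumption, but it gives 17 × 2 + 2 × 1 = 36 units, and its SD rounds to 0.3.

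Working backwards with the normal approximation, the SD for which 33 per group gives exactly 80% power is 0.22 / (√(2/33) × 2.802) = 0.319. A one-sided test raises this only to 0.22 / (0.246 × 2.486) = 0.36. Neither is near 0.5.

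**Step 3: what 33 per group delivers at the stated SD of 0.5.** (two-sided 5%)

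| Difference | Power at 33 per group (t) | n per group for 80% power (normal approx.) |
|---|---|---|
| 0.22 (Study duration) | 42% | 82 |
| 0.15 (Design) | about 22% | 175 |

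The difference detectable with 80% power is 0.5 × √(2/33) × 2.802 = 0.34 units (0.35 with t).

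**Step 4: can the effect of the wider window be derived?** Take the 17/2 split for the 19 women and add early women under two opposite assumptions. Power is t-based, at 33 per group, for a difference of 0.22.

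| Early women added | Units counted for each | Mean | SD | Power |
|---|---|---|---|---|
| 0 | – | 1.89 | 0.315 | 80% |
| 4 | 2, non-acute only | 1.91 | 0.29 | 86% |
| 4 | two with 1, two with 2, non-acute only | 1.83 | 0.39 | 62% |
| 4 | 3.45, all units, no spread among them | 2.17 | 0.67 | 26% |

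The documents give neither the number of early women who qualify nor their units after 6 hours. Both the size and the direction of the change therefore depend on missing data.

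**The case against.** The strongest reply is that the SD of 0.5 is already about two-thirds wider than the baseline 0.3 (0.5/0.3 = 1.67) and so may allow for a broader population. It would also cover the non-acute-only examples above. That defends 0.5 as a planning value, but not 33, which does not follow from 0.5.

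A second reply is that the groups overlap. Earlier-transfused women would qualify through later, non-acute units, in a setting where 2 units were the usual practice, and the exclusions (instability, hemoglobin below 5 g/dL, a judged definite need for 2 units) plausibly remove heavier users. This stands. A reader might infer from the 3.45 units per omitted woman that enrolling from 6 hours must raise the mean and SD and push power far below 42%. The documents do not support that: the 3.45 includes acute units, and the SD could fall.

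Third, the procedures attachment, which is not among the documents reviewed, may define which units count, and a 2015 judgement that a woman definitely needed 2 units may not be recoverable from charts. Both points limit the fix but do not remove the need for it.

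**Conclusion.** The point holds in a limited form. The planning mean and the only sourced SD describe women not transfused in the first 12 hours, a narrower group than the one the trial enrols, and the protocol itself says so for some women. The stated SD of 0.5 has no source, and the figure of 33 is consistent only with an SD close to that of the narrow group. At the stated inputs the power is about 42%, not 80%, assuming a two-sided 5% t test, equal SDs and no dropout.

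A reader might go further and say that the 80% claim fails because it rests on the wrong population. That is too strong. The claim fails first on its own arithmetic, whatever the population, and the two groups overlap. The mismatch adds an uncertainty that the documents do not allow one to size or sign; correcting 33 to 82 or 83 would still leave an unsourced SD and a mean from a different time window.

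**What to change.** 1. From the 2015 audit, as far as the charts allow, re-tabulate the mean and SD of units started 6 hours or more after delivery. Include women with an earlier acute transfusion, and apply those inclusion and exclusion criteria that can be recovered. State which could not be.
2. Use one SD with its source in place of 0.3 and 0.5.
3. Reconcile the targets of 1.68 and 1.75 across Design, Study duration and Accrual.
4. Restate the power, or the detectable difference, for 33 per group, with sidedness given.
5. Define the primary endpoint as units started after randomisation, so that acute units given earlier do not add variance unrelated to the allocated protocol.

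The cost is a short re-tabulation of a 30-woman audit, provided that unit timing is in the charts, plus a revised sample-size paragraph in two places and one sentence on the endpoint. No more patients are needed. The price is a stated power that will probably be less favourable than 80%: on the present inputs, about 42% for 0.22 units, or 80% only for a difference of about 0.35.

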Through the Council for Patient Safety in Womens Health, the primary investigator won a National Improvement Challenge Award for work in postpartum hemorrhage. This award totaled \$3000 designated for future work in this realm. We plan to utilize this funding for patient compensation as a part of this trial. Given we ask the patient to return for a study visit to complete survey data, we plan to compensate patients for the time and effort involved in participating in this study. We plan to provide the patient with \$25 on discharge date from delivery hospitalization and \$25 at the time of the 4-9 week postpartum End of Study Visit once the survey instruments are complete. This will be provided in the form of a Visa giftcard.

Study Procedures

Suicidal Ideation and Behavior

Does this research qualify as a clinical investigation that will utilize a test article (ie- drug or biological) which may carry a potential for central nervous system (CNS) effect(s)?

No

Procedures

See attached document.

The following documents are currently attached to this item:

Procedures (smartbloodprotocolforirbv2.pptx)

Deception

Does your project use deception?

No

International Research

Are you conducting research outside of the United States?

No

Analysis Plan

Baseline and demographic characteristics will be summarized by standard descriptive statistics (including mean and standard deviation for continuous variables such as age and standard percentages for categorical variables such as gender). We will use T tests to compare number of units transfused between our single-unit and multiple-unit transfusion protocols.

The following documents are currently attached to this item:

There are no documents attached for this item.

Data confidentiality

- x **Paper-based records will be kept in a secure location and only be accessible to personnel involved in the study.**
- x **Computer-based files will only be made available to personnel involved in the study through the use of access privileges and passwords.**

Prior to access to any study-related information, personnel will be required to sign statements agreeing to protect the security and confidentiality of identifiable information.

- x **Wherever feasible, identifiers will be removed from study-related information.**

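### 33 per group gives 42% (two-sided) or 55% (one-sided) power for 1.9 to 1.68 units at SD 0.5, not 80%, and the primary endpoint names a different target (1.75)

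*Combined protocol and SAP*

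**What the plan says.** The sample-size statement stands under Study Design, Study duration, and is repeated under Characteristics of the Study Population, Accrual. It claims "80% power to demonstrate a reduction in number of blood products used per person from 1.9 to 1.68 with a SD of 0.5". The group size given for that claim is 33, with alpha set at 5%. The listed enrolment of 66 matches 33 per group, and randomization is 1:1.

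Both sections also give the baseline data behind the calculation: 36 units among 19 patients, or "1.9 units per person transfused (with a standard deviation [SD] of 0.3".

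Under Study Design, Design, the endpoint is worded with another target: "The primary study endpoint will be a reduction in number of blood products used per person from 1.9 to 1.75 with a SD of 0.5".

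The Analysis Plan names the test: "We will use T tests to compare number of units transfused between our single-unit and multiple-unit transfusion protocols". The documents do not say whether the 5% is one- or two-sided, and they give no allowance for dropout.

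**The concern.** A difference of 0.22 with an SD of 0.5 is a standardized effect of 0.44. Thirty-three per group is far too few for 80% power at that effect size. The two stated targets also differ: 0.22 units in the sample-size text and 0.15 in the endpoint definition.

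This is the primary comparison, and the 80% figure is the only justification given for enrolling 66 women. A null result would be read as coming from a trial with a 20% chance of missing its target difference. If the means are 1.9 and 1.68 and the SD is 0.5, that chance is 58% two-sided or 45% one-sided. A reader also cannot tell which reduction the trial was sized to find.

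**Working it through.** **Inputs.** Control mean 1.9, target 1.68, SD 0.5, alpha 5%, power 80% and 33 per group (Study duration; Accrual). Alternative target 1.75 at SD 0.5, and 1:1 allocation (Design). Two-sample t test (Analysis Plan). Baseline SD 0.3 (Study duration; Accrual). Both one- and two-sided tests were tried because the plan does not say.

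**1. Can 33 be reproduced from the stated inputs?** The normal approximation is n per group = 2 × SD² × (z_alpha + z_power)² / difference².
- Two-sided: 2 × 0.25 × (1.960 + 0.842)² / 0.22² = 81.1, so 82. The noncentral t gives 82.05, so 83.
- One-sided: 2 × 0.25 × (1.645 + 0.842)² / 0.22² = 63.9, so 64. The noncentral t gives 64.56, so 65.

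Neither gives 33.

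**2. Power at 33 per group for 1.68.** The standard error is 0.5 × √(2/33) = 0.123, and 0.22 / 0.123 = 1.787.
- Normal approximation: Φ(1.787 − 1.960) = 43% two-sided; Φ(1.787 − 1.645) = 56% one-sided.
- Noncentral t on 64 degrees of freedom: 42.1% two-sided; 54.9% one-sided.

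**3. Difference detectable with 80% power at 33 per group and SD 0.5 (t test).** 0.350 units two-sided or 0.309 one-sided, against the stated 0.22.

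**4. The other target, 1.75.** The difference is 0.15 and the standardized effect 0.30. Power at 33 per group is 22% two-sided or 33% one-sided. For 80% power the t test needs 176 or 139 per group.

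**5. Could the calculation have used the baseline SD of 0.3?** With 0.3 in both arms, 1.9 versus 1.68 needs 31 per group two-sided, and 33 per group gives 83.5% two-sided or 90.4% one-sided. That is near the claim, but an SD of 0.3 is not attainable in the arm averaging 1.68. A whole-number count with mean 1 + f has variance of at least f(1 − f), reached when every patient receives one or two units:
- mean 1.9: √(0.9 × 0.1) = 0.300
- mean 1.68: √(0.68 × 0.32) = 0.466

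The pooled minimum is √((0.300² + 0.466²)/2) = 0.392. At that SD, 33 per group gives 61.2% two-sided or 72.9% one-sided, and 80% needs 51 or 40 per group. A simulation of one-or-two-unit outcomes with these means (100,000 trials, pooled t test) gave 62% and 72%.

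**Summary, t test at 33 per group**

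| Target | SD | Two-sided | One-sided |
|---|---|---|---|
| 1.68 | 0.5 (as stated) | 42% | 55% |
| 1.68 | 0.300 / 0.466 (smallest possible) | 61% | 73% |
| 1.68 | 0.3 in both arms (not attainable) | 83% | 90% |
| 1.75 | 0.5 (as stated) | 22% | 33% |
| 1.75 | 0.3 in both arms (not attainable) | 52% | 64% |

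**The case against.** The best defence is that the calculation was really run with the baseline SD of 0.3 and that the printed 0.5 is a slip. The 83.5% two-sided figure makes this plausible, though the documents cannot settle it. It does not save the statement. An SD of 0.5 is printed in all three places that give a target, and 0.3 is below the smallest SD possible for whole units averaging 1.68. That bound assumes that only whole units are counted. The documents do not say so outright, but they report units as counts throughout.

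A second point is that the hypothesis is directional, so a one-sided test may have been meant. That raises power to 55% at the stated SD and 73% in the best case, still short of 80%.

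Third, the protocol never claims 80% power for 1.75. This is fair. The 22% and 33% figures show what the endpoint wording implies, and the fault there is the conflict between the two targets.

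Fourth, the shortfall is conditional on the stated target. If the single-unit mean were 1.6 with one-or-two-unit outcomes at their minimum SDs, 33 per group would have about 84% power two-sided. This also stands: the check shows that the stated calculation is wrong, not that the trial must fail to find a larger effect. The documents do not say that 1.6 is expected.

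**Conclusion.** The power statement is wrong as written. With the stated means, SD and alpha and the planned t test, 33 per group gives 42% power two-sided or 55% one-sided, about half to two thirds of the claimed 80%. Under the most favourable SDs that whole units allow, it reaches about 61% or 73%. No choice of sidedness with an attainable SD brings 1.9 versus 1.68 to 80%. Separately, the targets 1.68 and 1.75 contradict each other, whatever SD or sidedness is chosen. These results assume full follow-up for the primary outcome; losses would lower the power further. Where the 33 came from cannot be determined from the documents.

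**What to change.** Choose one target difference and use it in Design (Primary Study Endpoint), Study duration and Accrual. State the planning SD with its basis, and say whether the 5% is one- or two-sided. Then restate the power in Study duration and Accrual.

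Illustrative wording, if SD 0.5 and a two-sided test are kept: *With 33 patients per group, a two-sample t test at two-sided 5% and SD 0.5 has 42% power for 1.9 versus 1.68 units, and 80% power for a difference of 0.35 units (1.9 versus 1.55).* If 1.75 is the target kept, the corresponding power is 22%. If the test is one-sided, the figures are 55% for 1.68, 33% for 1.75, and a detectable difference of 0.31.

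This costs text edits in three places and a less favourable power figure; enrolment need not change. Whether to accept that power, justify a larger target or enlarge the trial is for the investigators to decide. Enlarging is expensive. The protocol expects 72 eligible patients a year with 50% agreeing, or 36 a year. For 1.68 at SD 0.5, 2 × 83 = 166 patients would take 166/36 = 4.6 years (two-sided), and 2 × 65 = 130 would take 130/36 = 3.6 years (one-sided), against the 2 years planned.

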Postpartum hemorrhage (PPH), which accounts for 30% of all direct maternal deaths, is the single most important cause of maternal morbidity and mortality across the globe (1) and is a focus of attention of national organizations such as the Council for Patient Safety in Womens Health in recent years. Yet, there remains a paucity of data on the appropriate management of non-acute postpartum anemia. Packed red blood cells (pRBC) transfusion may be a lifesaving treatment for acute hemorrhage, but it is also widely used after PPH for non-acute, stable anemia (2). Postpartum anemia is associated with clinical consequences including fatigue and symptoms of depression (3,4). A low postpartum hemoglobin (Hb) is the most important commonly cited reason to prescribe RBC transfusions (5). The indication for RBC transfusion, however, is not to increase postpartum Hb level, but to reduce morbidity and improve the health-related quality of life. It is common practice in obstetrics to offer a transfusion of pRBCs to women with a Hb value less than 7 g/dL (hematocrit less than 20%) and to symptomatic women with even higher hemoglobin levels (2). Transfusions were historically initiated with 2 units of pRBCs, and this remains the case on many labor and delivery units across the country, including at the Hospital of the University of Pennsylvania. However, there is increasing concern about adverse effects and costs of current transfusion practice. The most recent recommendation from the American Association of Blood Banks (AABB) for a stable patient is to begin with 1 unit and reassess (6). The American College of Obstetricians and Gynecologists, in the newly released 2017 practice bulletin on postpartum hemorrhage, has included the AABBs statement, endorsing the use of single-unit transfusion (7). While surgical data has successfully demonstrated that liberal blood transfusion increases morbidity and mortality in comparison to restricted transfusion (8), no trials have been performed in obstetrics to demonstrate superiority of a single-unit transfusion protocol. In addition, a qualitative study in Australia looking at provider practice and perception regarding single- versus multiple- unit transfusion protocols after a similar national recommendation demonstrated wide variation. To some providers, single-unit transfusions had lower perceived utility and multiple-unit transfusions were perceived to improve maternal-infant bonding and infectious outcomes. In contrast, others believed that single-unit transfusions reduced infection and transfusion reaction risk while having the same desired efficacy (9).

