Women over 18 Willing and stable to give consent 6 hours postpartum from any mode of delivery Determined by their physician to require blood transfusion either by: o Hb 7g/dL OR o 7g/dL with any sign or symptom of anemia such as fatigue, dizziness, tachycardia, or hypotension Agreed to accept blood transfusion No contraindications to blood transfusion

Key exclusion criteria

We plan to exclude: 1. Patients with hemoglobinopathies 2. Patients with an ejection fraction 35% 3. Patients presenting with heart rate of greater than 130 bpm and/or blood pressure readings of less than 80/40 mm Hg. 4. Patients whose clinicians determine that they do not require transfusion. 5. Patients whose clinicians determine that they will definitely require 2 units. 6. Patients who present with hemoglobin levels of less than 5g/dL.

Vulnerable Populations

Children Form
 
Pregnant women (if the study procedures may affect the condition of the pregnant woman or fetus) Form
 
Fetuses and/or Neonates Form
 
Prisoners Form
 
Other
 
 None of the above populations are included in the research study

--

The following documents are currently attached to this item:

There are no documents attached for this item.

Populations vulnerable to undue influence or coercion

Informed consent will be obtained without coercion and all patients approached will be treated equally. The Maternal Child Health Research Program works to ensure that studies do not compete for participants and that the patient experience on labor and delivery is not negatively impacted by the research agenda. Penn students or employees approached to consent will be informed that their decision whether or not to participate will in no way impact their standing at the university.

Subject recruitment

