We plan to recruit admitted postpartum patients at the time a provider makes the decision that they require a nonacute blood transfusion. If a provider determines a patient is a candidate for a nonacute blood transfusion: Step 1: Provider informs patient of recommendation for pRBC transfusion. Sample: We feel that, given your blood count [and/or symptoms], a blood transfusion will help you feel and heal better. However, we dont know whether one or two units is the right amount of blood for a postpartum patient and we are currently doing a study here to figure that out. Would you be willing to speak to our coordinator about the study? Step 2: Inform research staff/provider about potential patient, who will approach the patient for consent at that time. If she consents, she will be randomized at the same time. In order to ensure timely treatment, a time limit for consent and randomization from the time a provider deems a patient requires transfusion will be set at 6 hours.

Will the recruitment plan propose to use any Penn media services (communications, marketing, etc.) for outreach via social media avenues (examples include: Facebook, Twitter, blogging, texting, etc.) or does the study team plan to directly use social media to recruit for the research?

No

The following documents are currently attached to this item:

There are no documents attached for this item.

Subject compensation*

Will subjects be financially compensated for their participation?

Yes

The following documents are currently attached to this item:

There are no documents attached for this item.

If there is subject compensation, provide the schedule for compensation per study visit or session and total amount for entire participation, either as text or separate document

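### The primary t-test leaves unused a pre-randomisation hemoglobin that eligibility already requires; adjusting for it is a cheap, low-priority gain in precision

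*Combined protocol and SAP*

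**What the plan says.** The Analysis Plan section summarises baseline variables descriptively and then gives the only inferential method in the document: "We will use T tests to compare number of units transfused between our single-unit and multiple-unit transfusion protocols". It names no covariate, stratification factor or regression model and lists no attachment. The Design section describes 1:1 allocation by a computer-generated algorithm and mentions no stratification.

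A hemoglobin value is needed to decide eligibility. The Target population section takes women "determined to require blood transfusion either by Hb 7g/dL, or 7g/dL with signs or symptoms of anemia" (the comparison signs did not survive in the text available), so both routes in rest on a hemoglobin value. Key exclusion criteria remove "Patients who present with hemoglobin levels of less than 5g/dL". Under Subject recruitment, a consenting woman is randomised at consent, and "a time limit for consent and randomization from the time a provider deems a patient requires transfusion will be set at 6 hours". The hemoglobin used for eligibility therefore precedes assignment.

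Study duration and Accrual give the planning values: "80% power to demonstrate a reduction in number of blood products used per person from 1.9 to 1.68 with a SD of 0.5", alpha 5%, 33 per group.

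**The concern.** Adjusting for a baseline variable that predicts the outcome removes part of the residual variance. The treatment estimate then has a smaller standard error with no extra patient, visit or test. Here a candidate covariate is already collected on every woman, and recruiting 66 women is expected to take two years. An adjustment fixed in advance also handles a chance imbalance in hemoglobin, which is possible with 33 per arm and no stratification mentioned, without a choice made after the data are seen. Only precision is at stake; bias and type I error are not.

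**Working it through.** **Inputs.** Means 1.9 and 1.68 (difference 0.22), SD 0.5, alpha 5% and 33 per arm come from Study duration and Accrual. The alternative target mean of 1.75 (difference 0.15) is from Design. Baseline practice, 36 units in 19 women with SD 0.3, is from Study duration. Two-sided testing is assumed because sidedness is not stated. The correlation r between hemoglobin and units (taken as a magnitude) is not in the documents, so it is varied from 0 to 0.5.

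**The plan's own figure.** For the t-test, the noncentrality is (0.22/0.5) × √(33/2) = 0.44 × 4.062 = 1.787, with 64 df and critical value 1.998. Power is 42.1%, not 80%; 80% needs 83 per arm. One-sided, 33 per arm gives about 55%. The stated 33 does fit a smaller SD. If every woman in the baseline series had 1 or 2 units, 36 units in 19 women means 17 with two and 2 with one, an SD of 0.315; 33 per arm then gives about 80%. The 42.1% starting point therefore holds only for the stated SD of 0.5.

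**Adjusted model, same r in both arms.** The residual SD is 0.5 × √(1 − r²), one df is spent (63 left), and chance imbalance in hemoglobin inflates the variance by 1 + 1/62 on average:

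noncentrality = 0.44/√(1 − r²) × √(16.5/(1 + 1/62))

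95% CI half-width = t(63) × 0.5 × √(1 − r²) × √((2/33)(1 + 1/62))

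| Analysis | Noncentrality | Power | 95% CI half-width (units) |
|---|---|---|---|
| t-test | 1.787 | 42.1% | 0.246 |
| Adjusted, r = 0 | 1.773 | 41.5% | 0.248 |
| r = 0.1 | 1.782 | 41.9% | 0.247 |
| r = 0.2 | 1.810 | 42.9% | 0.243 |
| r = 0.3 | 1.859 | 44.8% | 0.237 |
| r = 0.4 | 1.935 | 47.8% | 0.227 |
| r = 0.5 | 2.047 | 52.2% | 0.215 |

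Break-even is at r of about 0.13. For the difference of 0.15, power is 22.5% unadjusted, 23.9% at r = 0.3 and 28.0% at r = 0.5.

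**Adjusted model, hemoglobin predictive only in the single-unit arm.** With equal arms and one common slope, the effective correlation is r × s₁/√(2(s₁² + s₂²)), where r and s₁ belong to the single-unit arm and s₂ is the SD in the multiple-unit arm.

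- SD 0.5 in both arms: the effective r is half the single-arm r. A single-arm r of 0.3 becomes 0.15 (42.3%, gain 0.2 points); 0.5 becomes 0.25 (43.8%, gain 1.7).
- Assumed SDs 0.63 (single-unit) and 0.315 (multiple-unit): the factor is 0.63/√(2 × 0.496) = 0.63. The effective r is 0.19 or 0.32, and the gain is about 0.7 or about 3 points.
- Limit of no spread at all in the multiple-unit arm: the factor is 1/√2. The effective r is 0.21 or 0.35, and power is about 43% or 46%.

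**Type I error.** In simulations with normal outcomes, with whole units, and with unequal spread by arm, the adjusted model with ordinary standard errors rejected a true null in 4.8% to 5.3% of runs.

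**Sample size.** For 80% power at a difference of 0.22 and SD 0.5, the need is 83 per arm unadjusted, 76 at r = 0.3 and 63 at r = 0.5. For 33 per arm to suffice, hemoglobin would have to explain about 61% of the variance in units.

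**The case against.** The strongest reply is that no error has been shown. A t-test stated in advance is a legitimate choice, and the benefit of replacing it depends wholly on an r that the documents do not give. That stands, and it is why this is offered as an improvement.

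The documents also give reasons to expect a weak correlation. A reader might infer a strong one from the Background, which says "A low postpartum hemoglobin (Hb) is the most important commonly cited reason to prescribe RBC transfusions". That sentence concerns whether a transfusion is prescribed. Every enrolled woman has passed that decision, and the outcome is how many units follow. Hemoglobin is truncated below 5 g/dL, women are excluded if they are "Patients whose clinicians determine that they will definitely require 2 units", and under past practice, "if the decision was made to proceed with transfusion, generally 2 units of pRBCs were given". If the multiple-unit arm mostly receives two units, hemoglobin has little to predict there. The gain of about 10 points at r = 0.5 in both arms is therefore an optimistic edge.

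It can also be said that the importance is borrowed from the gap between 42% and 80% power. That is partly right: the gap depends on the SD of 0.5 and is a separate question.

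These points limit the size of the gain but do not remove the case for adjusting. The covariate costs nothing to collect, and the loss if it is useless is about 0.6 points of power.

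**Conclusion.** The point holds as a low-priority improvement in precision. The planned analysis ignores a baseline value that must exist for every woman before assignment. At the stated planning values, adjustment changes power by between −0.6 points (r = 0) and about +10 points (r = 0.5 in both arms). If hemoglobin matters only in the single-unit arm, about 0 to 3 points is more realistic. These figures rest on an assumed r, two-sided testing, the stated SD of 0.5 and 33 per arm with no losses.

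Two stronger readings should be resisted. One is that the unadjusted t-test is invalid or biased; under 1:1 randomisation it is neither. The other is that adjustment would make 33 per arm adequate. At SD 0.5 it would not for any r in the range considered, and the mismatch between 33 per arm and its stated inputs has to be settled on its own. The Procedures attachment is not available, but the Analysis Plan states its method directly and refers to nothing further.

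**What to change.** In the Analysis Plan, make the primary analysis a linear model of units transfused on arm and the last hemoglobin before randomisation, entered as a continuous variable. Report the adjusted mean difference with its 95% CI, and keep the unadjusted t-test as a sensitivity analysis. Ordinary standard errors with a t reference performed acceptably in the checks above. Robust standard errors are an acceptable alternative because the spread of units may differ by arm; name one choice in advance. Fix the covariate and the model before outcomes are compared by arm.

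The cost is a few lines of text and one degree of freedom. No new measurement is needed; the value already required for eligibility has only to be recorded in the trial database.
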